#### **9.2.1.1. RA Patient Treated with Tofacitinib**

1. Initiation of tofacitinib as captured in ARTIS/SRQ.
2. Diagnosis of rheumatoid arthritis by a consulting rheumatologist.

#### **9.2.1.2. RA Patients Treated with bDMARD:**

1. Initiation of a bDMARD therapy as captured in ARTIS/SRQ.
2. Diagnosis of rheumatoid arthritis by a consulting rheumatologist.
3. Aged 18 years and older.

---

 Diagnosis of RA by a consulting rheumatologist is possible for all patients with the exception of the bio-naïve patients and the general population cohorts proposed as comparator populations.

4. To ensure a contemporaneous cohort, diagnosis of RA must have occurred after 01 January 2012.

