## 6. MILESTONES

Milestone	Planned date
-----------	--------------

Registration in the EU PAS register	01 September 2019
Start of data collection	15 September 2019
Interim report	14 March 2021
Interim report	14 March 2023
Interim report	14 March 2025
End of data collection	14 September 2025
Final Study Report	14 August 2026

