### **9.2.1. Inclusion Criteria**

The active surveillance population includes RA patients enrolled in the ARTIS register who are newly treated with tofacitinib following EMA approval and Swedish launch of the product (product fully available April 2017). For contextualization purposes, the study population will also include the comparator cohorts as defined in inclusion/exclusion criteria. Patient consent is not applicable; planned analyses use data from existing data sources that do not include patient identifiers. Patients are eligible to move between cohorts if inclusion/exclusion criteria are met.

Patients must meet all of the following inclusion criteria to be eligible for inclusion in the study:

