### **9.9. Limitations of the Research Methods**

This study is designed to monitor the safety of tofacitinib within the clinical practice setting utilizing the ARTIS Register, a well-established Swedish-based rheumatology register. Despite the strengths of the register, data must be evaluated in light of their limitations. For example, consistent with most observational studies, the possibility of channeling and endpoint misclassification, are of concern in interpreting findings.

As a new therapy in the RA treatment armamentarium, it is possible that patients treated with tofacitinib will represent those with the most severe cases of disease, longer disease duration,

history of multiple failed RA therapies and physical comorbidities that place patients at risk for events. Biases resulting from channeling may present as increased rates of safety events of interest in the early phases of the study. Comparison to internal comparators may illuminate such channeling. Stratification on key indicators of disease severity, patient characteristics and past therapies can be done for contextualization. Trend analyses may be conducted to evaluate rates in tofacitinib patients over time.

The RA treatment landscape has evolved over time with the introduction of new therapies, treatment recommendations, and approaches to patient management. The rates of safety events of interest and their distribution among patient-types may have changed over time. The comparators in this study are not exclusively contemporaneous to tofacitinib treated patients. Analysis may be unable to identify or control for any changes in rates due to changes in the treatment landscape.

Event misclassification is of particular concern within the observational setting due to less stringent monitoring relative to clinical trials. While ARTIS has an established system to identify and capture endpoint data, all events cannot be fully verified via source documentation. Instead, linkage to national health care registers allows the register to obtain data on all safety events of interest (regardless of suspected causal relationship to the treatments), and on comparator cohorts, so that any potential risk increases can be evaluated in light of risks among patients and with other treatments, and the general Swedish population.

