
Notes: Analysis was only made for comparisons where both cohort had at least 5 observed events. HR: Hazard Ratio. CI: Confidence Interval.  HRa: stratified for year at start, adjusted for age and sex.  HRb: stratified for year at start, adjusted for age, sex, prior number of days in inpatient care, history of infection, cancer, MI, diabetes, COPD, and joint replacement surgery.  HRc: stratified for year at start, adjusted for age, sex, prior number of days in inpatient care, history of infection, cancer, MI, diabetes, COPD, and joint replacement surgery, Rheumatoid factor, HAQ(linear), RA disease duration, DAS28(linear), DMARDs, steroids. Complete case analysis.  HRd: as HRc but using a missing indicator, and quartiles, for HAQ and DAS28.
									

Table IV. Results from crude and adjusted Cox regressions comparing tofacitinib to biologic DMARDs (bDMARDs), stratified by the number of bDMARDs									
Outcome	Number of previous biologics	HRa	95% CI	HRb	95% CI	HRc	95% CI	HRd	95% CI
Each event	0								
	1								
	2								
	Aggregate estimate								

Notes: Analysis was only made for comparisons where both cohorts had at least 5 observed events. HR: Hazard Ratio. CI: Confidence Interval.  HRa: stratified for year at start, adjusted for age and sex.  HRb: stratified for year at start, adjusted for age, sex, prior number of days in inpatient care, history of infection, cancer, MI, diabetes, COPD, and joint replacement surgery.  HRc: stratified for year at start, adjusted for age, sex, prior number of days in inpatient care, history of infection, cancer, MI, diabetes, COPD, and joint replacement surgery, Rheumatoid factor, HAQ(linear), RA disease duration, DAS28(linear), DMARDs, steroids. Complete case analysis.
									

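### The 2012 diagnosis-date rule meant to make the comparators contemporaneous applies to the two RA comparator cohorts only, and limits disease duration rather than the date of treatment start

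*Protocol*

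**What the plan says.** Section 9.2.1.1 gives the tofacitinib cohort two criteria: "Initiation of tofacitinib as captured in ARTIS/SRQ" and "Diagnosis of rheumatoid arthritis by a consulting rheumatologist". Neither limits when RA was diagnosed. Section 9.2.1 dates the Swedish launch: "product fully available April 2017".

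Section 9.2.1.2 admits bDMARD patients on "Initiation of a bDMARD therapy as captured in ARTIS/SRQ", with no calendar limit on that start, and adds "To ensure a contemporaneous cohort, diagnosis of RA must have occurred after 01 January 2012". Section 9.2.1.3 sets the same diagnosis rule for the ts/bDMARD-naïve cohort, again with no limit on the index date. Section 9.2.2 adds no exclusion that would change this.

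Section 9.9 says "The comparators in this study are not exclusively contemporaneous to tofacitinib treated patients" and expects that tofacitinib patients may have more severe and longer-standing disease and several failed therapies. Section 9.3.2 reasons from the expectation that most tofacitinib patients were in the bDMARD cohort before they switched.

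Section 9.7.2 plans crude and age/sex-standardised rates. In Appendix 2, the simplest Cox model is "HRa: stratified for year at start, adjusted for age and sex". RA disease duration enters only in HRc and HRd.

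**The concern.** Follow-up runs from treatment start, or from an index date in cohorts not defined by a drug (Section 9.3.2). Whether a comparator is contemporaneous therefore depends on that date. A rule on diagnosis date excludes starts before 2012 but does not align the cohorts after that.

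The rule also has a side effect in one direction only. It removes comparators with long-standing RA and leaves tofacitinib patients with long-standing RA in place. Years since diagnosis go with prior treatment, accumulated comorbidity and exposure to earlier drugs. If event risk rises with duration at a given age and sex (an assumption here, though Section 9.9 treats longer duration as part of channeling), tofacitinib rates will look high against the RA comparators for reasons unrelated to the drug. A real signal could equally be put down to channeling, because the comparators that would separate the two explanations have been removed.

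**Working it through.** **Inputs.** Diagnosis limit 1 January 2012 (Sections 9.2.1.2 and 9.2.1.3). Earliest general tofacitinib availability April 2017 (Section 9.2.1), taken as 1 April. Start of data collection 15 September 2019, and "End of data collection 14 September 2025" (Section 6). The protocol states no figure of its own on this point.

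**1. Longest possible RA duration at index** = index date − 1 January 2012.

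| Index date | bDMARD and naïve cohorts | Tofacitinib cohort |
|---|---|---|
| 1 April 2017 | 5.25 years | no limit |
| 15 September 2019 | 7.7 years | no limit |
| 14 September 2025 | 13.7 years | no limit |

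**2. Share of bDMARD starts that can precede any tofacitinib start.** The pre-launch window is 5.25 years of a 13.7-year entry window. The share of starts depends on accrual, which the protocol does not give.
- Constant accrual from 1 January 2012: 5.25 / 13.7 = 0.38.
- Accrual rising linearly from zero: (5.25 / 13.7)² = 0.15.

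Constant accrual is the less plausible end. On 1 January 2012 nobody has yet been diagnosed after that date, so the eligible pool starts empty and grows.

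**3. Consistency with Section 9.3.2.** A tofacitinib patient diagnosed before 2012 fails criterion 4 of Section 9.2.1.2 and can never have been in the bDMARD cohort, whatever biologics were used earlier. The expectation that most tofacitinib patients came through that cohort therefore holds only if most were diagnosed after 1 January 2012. The protocol does not say so.

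**4. What each planned analysis does about duration.**
- Crude and age/sex-standardised rates: nothing directly.
- HRa and HRb: stratified by start year, without duration.
- HRc and HRd: adjusted for duration. At a given start year, however, no comparator has a duration above the cap in step 1, so beyond it the adjustment rests on the fitted form of the covariate.

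**The case against.** The protocol is a descriptive study with no prior hypotheses. The comparators give context, and the Cox analysis is conditional on feasibility. Several safeguards exist. Section 9.7.2 makes feasibility depend on suitable overlap between exposure groups and allows propensity score matching or inverse probability weighting. Appendix 2 reports disease duration and start year by cohort (Table I) and splits rates by number of previous biologics (Table II). All Cox models are stratified by start year. Section 9.9 discloses that the comparators are not all contemporaneous. A diagnosis limit also has a sensible purpose, since Table 1 shows disease activity at first biologic falling over time.

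Most of this stands as mitigation, but it is partial. Section 9.9 discloses calendar drift, not the one-sided cap on duration. Matching would drop tofacitinib patients without counterparts; it cannot supply the comparators. The split by previous biologics does not escape the cap either: an April 2017 third-biologic starter must have gone from diagnosis to a third biologic within 5.25 years. The overlap check governs the comparative report only, and descriptive rates are published whether or not it passes.

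Three stronger readings should be resisted.
- A reader might infer that bDMARD starters before 2017 add nothing to hazard ratios stratified by start year. They give no direct tofacitinib contrast, but covariate coefficients are shared across strata, so they do inform the confounder adjustment.
- A reader might want entry closed to all bDMARD starts before April 2017. That would discard follow-up which the once-exposed-always-at-risk analysis in Section 9.3.2 is designed to keep for long-latency events.
- A reader might use Section 9.2's figures to size the problem. Prevalence is 0.7% of 10 million = 70,000, and incidence is 41/100,000 = 4,100 per year. So at most 4,100 × 5.25 ≈ 21,500 patients, or 31% of prevalent RA in April 2017, could satisfy the rule. This describes all prevalent RA, not users of advanced therapy, and says nothing firm about the share of tofacitinib patients without a counterpart.

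**Conclusion.** The point holds on the text. The diagnosis-date rule is asymmetric, does not secure the contemporaneity it is written for, and caps disease duration in the bDMARD and naïve cohorts alone at 5.25 years (April 2017 index) to 13.7 years (September 2025). It sits badly with the protocol's own expectations of longer duration in tofacitinib patients and of prior membership of the bDMARD cohort. The general population cohort is unaffected.

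The size of the resulting bias cannot be computed, because no duration distribution by cohort is given. Its direction, against tofacitinib, follows only if risk increases with duration after age and sex are accounted for. The share of bDMARD starts before launch is about 15% to 38% across the two accrual assumptions, and the upper figure should not be quoted alone. The text does not show that the planned hazard ratios are invalid. It shows that the descriptive rates, which are the core deliverable, carry an avoidable imbalance, and that the adjusted models cannot fully remove it.

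**What to change.** 1. In Sections 9.2.1.1 to 9.2.1.3, apply one RA-diagnosis-date rule, or none, to all three RA cohorts. At minimum, add a sensitivity analysis restricted to tofacitinib patients diagnosed after 1 January 2012, so that both sides have the same cap at a given index date.
2. Keep the 2012–2017 bDMARD starters for the once-exposed-always-at-risk analysis. In addition, report bDMARD and naïve rates restricted to, or stratified by, index date on or after April 2017, and label this as the contemporaneous comparison. Both steps are needed: the first aligns diagnosis dates, the second aligns calendar time.
3. Reconcile Section 9.3.2's expectation about prior bDMARD cohort membership with whichever rule is chosen, and state the duration cap in Section 9.9 if it is kept.

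The cost is amendment wording and a re-cut of comparator data already in the registers. Numbers fall in the restricted analyses. Section 9.5 describes the comparator groups as much larger than the tofacitinib group, so the loss matters most where tofacitinib patients are restricted: only 344 are projected in the first 24 months. Restricting the comparators by index date also shortens follow-up for late-appearing outcomes, which is why the unrestricted analysis should stay alongside.

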#### **9.2.1.3. ts/bDMARD-naïve RA Cohort**

- At least two separate visits documented in Swedish Patient Register listing RA as a diagnosis code for the visit, with at least one visit at a unit of Rheumatology or Internal Medicine.
- Patients are censored from this cohort when they start tofacitinib or a bDMARD, but are eligible for subsequent inclusion into the respective drug-based cohorts defined above.
- To ensure a contemporaneous cohort, diagnosis of RA must have occurred after 01 January 2012.

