**Objectives:** To estimate the rates of serious infections, malignancy (overall, excluding NMSC), subtypes of lymphoma, lung cancer, CV events, major adverse cardiovascular events (MACE), myocardial infarction (MI), venous thromboembolism (VTE; deep venous thrombosis [DVT] and pulmonary embolism [PE]) and other safety events of interest, including fractures, among patients with RA in Sweden who initiate tofacitinib. Rates will also be estimated among RA patients who initiate biologic DMARDs (bDMARDs), bDMARD and targeted synthetic DMARD (tsDMARD) naïve RA patients, and the general population to provide context for tofacitinib rates. Pending feasibility, a comparative analysis is planned as a secondary objective. Pending feasibility, rates of malignancy (overall, excluding NMSC), subtypes of lymphoma, lung cancer, serious infection, CV events, MACE, MI, VTE, and other event rates, including fracture, will be compared between tofacitinib-treated RA patients and the comparator cohort using methods that adjust for sex, age, year of treatment start, treatment history, disease severity, comorbidities, and other potential confounders. In response to the June 2021 signal evaluation procedure, subtypes of lymphoma, lung cancer, and MACE have been added as study endpoints (MI and lymphoma (overall) were already included as a study endpoints). Further, rates of events, including serious infections, MACE, MI, VTE and malignancies excluding NMSC, will be estimated in elderly patients aged 65 years and older.

**Study Design:** This active surveillance study will use existing data from the existing ARTIS register, an ongoing, prospective, observational, disease-based cohort started in 1999 with the primary aim of studying the safety of new therapies for RA during routine post-marketed clinical use.

**Population:** The study population will comprise all patients with RA enrolled within the ARTIS register who receive tofacitinib following EU approval and marketing, through the end of the study period. Three comparator cohorts will be assembled for risk characterization purposes: (1) RA patients who are treated with bDMARD (2) RA patients who are naïve to bDMARDs and tsDMARDs, and (3) a general population cohort.

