### Objectives:

To estimate the rates of serious infections, malignancy (overall, excluding NMSC), lung cancer, subtypes of lymphoma, CV events MACE and MI, VTE (DVT and PE) and other safety events of interest, including fractures, among patients with RA in Sweden who initiate tofacitinib. Rates will also be estimated among 1) patients with RA who have not been treated with bDMARD or tsDMARD, 2) patients with RA who initiate bDMARDs, and 3) the general population to provide context for rates observed on tofacitinib. Pending feasibility, rates of malignancy (overall, excluding NMSC), lung cancer, subtypes of lymphoma, serious infection, CV events, MACE MI, VTE, and other event rates, including fractures, will be compared between tofacitinib-treated RA patients and other comparator cohorts using multivariable Cox regressions adjusting for sex, age, year of treatment start, treatment history, disease severity, comorbidities and other potential confounders for more refined evaluation of safety concerns. In response to the June 2021 signal evaluation procedure, subtypes of lymphoma, lung cancer, and MACE have been added as study endpoints (MI and lymphoma (overall) were already included as a study endpoints). Further, rates of events, including serious infections, MACE, MI, VTE, and malignancies excluding NMSC, will be estimated in elderly patients aged 65 years and older.

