#### **9.2.2. Exclusion Criteria**

Patients meeting any of the following criteria will not be included in the study:

1. Patients not meeting the inclusion criteria for the respective cohorts will be excluded.

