### 9.3.2. Follow-Up

Subjects will be followed from treatment start (or for comparator cohorts not defined by therapy: from an index date) until each outcome of interest, with death and emigration from Sweden treated as censoring events.

Some outcomes of interest in this study are thought to potentially occur at a higher rate while on drug, but that increased risk subsides after the drug is discontinued (ie, serious infections, herpes zoster, CV events, gastrointestinal (GI) perforation, progressive multifocal leukoencephalopathy (PML)). Those events will be evaluated over a risk window that includes time from drug initiation until 90 days after end of treatment. When a patient initiates a new therapy within the 90-day extension, the time and events during the overlapping period will be assigned to both treatments. The 90-day extension period is implemented in part to accommodate ongoing exposure to treatments with longer half-lives, and in part to ensure that any subclinical or undiagnosed illness at time of end of treatment is captured. As an additional sensitivity analysis for MACE, MI, serious infection, VTE, herpes zoster, PML, and gastrointestinal perforation events with a 90-day extension period applied after treatment discontinuation, if a new medication is started during the 90-day window after discontinuation of a previous medication, initiation of the new medication will stop the 90-day risk window, and any event prior to the new medication start will be assigned to the discontinued medication. Similarly, as part of the primary analysis, for malignancy and all-cause mortality events, a 90-day risk window will be applied to the censoring at switch approach (i.e., if a malignancy or death occurs in first 90 days after a patient has switched to a different therapy, follow-up time and the event will be attributed to prior therapy and not current therapy).

For non-melanoma skin cancer (NMSC), lung cancer, lymphoma and malignancies excluding NMSC, and all-cause mortality, the manifestation of which is expected to be delayed relative to the time of exposure, the outcomes will be evaluated using two different approaches, a once exposed always at risk approach as the primary analysis and a censor at switch approach as a secondary analysis. PML rates will also be described using this approach.

---

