Using this primary analytic approach, if neither tofacitinib nor bDMARDs cause an increased risk of malignancy both exposure cohort rates will reflect the background rates of malignancy from the time of index to the end of the study period and the comparative effect measure will indicate no difference in rates. If tofacitinib does cause an increased rate of malignancy, which is the effect we are most interested in detecting, a relatively higher rate will be observed in the tofacitinib exposed cohort. The once exposed always at risk approach is therefore able to detect an increased rate given the non-random switching expected to occur given use of bDMARDs prior to tofacitinib and is consistent with previous studies evaluating the risk of individual biologics. Additional analyses will be conducted to evaluate potential confounders and the impact of different latency assumptions as will be described in the statistical analysis plan (SAP). Sensitivity analyses will be conducted that restrict the bDMARD comparator cohort to patients who were never exposed to tofacitinib or other non-biologic advanced therapies and compare the characteristics of those bDMARD patients ever and never exposed to tofacitinib.

Secondary analyses that censor follow up time after a switch to a different treatment class will also be performed. Among patients indexed to a bDMARD cohort, follow up will begin at index and continue until the first of an event, switch to tofacitinib or other non-biologic advanced systemic therapy, loss to follow up, death, or study end date. Similarly, for tofacitinib, follow up will begin at index and continue until the first of an event, switch to a non-JAK inhibitor-based advanced systemic therapy, loss to follow up, death or study end date. While this approach eliminates the problem of double counting, it may not allow sufficient follow up time to allow for latent effects or detection and decreases the number of events included reducing the statistical power to detect a higher risk of malignancy in tofacitinib treated patients. However, under an assumption of no latency or a very short latent period as in an aggressive tumor promoter, this approach would detect an increased risk of disease on tofacitinib relative to the risk due to bDMARDs.

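### The ts/bDMARD-naive cohort is censored only at tofacitinib or a bDMARD, so a patient who starts another tsDMARD stays in follow-up as naive, against the cohort's own definition.

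*Protocol*

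**What the plan says.** The definition covers the whole tsDMARD class wherever the cohort is formally described. The title of Protocol Section 9.2.1.3 is "ts/bDMARD-naïve RA Cohort". The abstract (Section 4) describes "RA patients who are naïve to bDMARDs and tsDMARDs", and the objectives (Section 8) describe "patients with RA who have not been treated with bDMARD or tsDMARD".

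The operational rule is narrower. The bullet in Section 9.2.1.3 reads "Patients are censored from this cohort when they start tofacitinib or a bDMARD", and goes on to allow those patients into the drug-based cohorts. No other tsDMARD is named.

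For the bDMARD cohort, the secondary censor-at-switch analysis in Section 9.3.2 ends follow-up at "switch to tofacitinib or other non-biologic advanced systemic therapy". In the same analysis, tofacitinib follow-up ends at "switch to a non-JAK inhibitor-based advanced systemic therapy".

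**The concern.** A comparator defined by non-exposure needs an exit rule that matches its definition. Here the definition excludes all tsDMARDs and the exit rule excludes one. An analyst who codes from the bullet would leave users of other tsDMARDs in the naive denominator, and their events in its numerator.

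The naive rates are there to put the tofacitinib rates in context. Section 8 also foresees, pending feasibility, adjusted Cox comparisons with the other comparator cohorts, and Table III in Appendix 2 is laid out for them. The outcomes include MACE, MI, lung cancer and lymphoma. If another drug of the class raises those risks, its events are credited to the unexposed side. That hides a difference, which is the unsafe direction for a safety study.

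**Working it through.** **Step 1. Definition against rule.**

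| Place in the protocol | Agents covered |
|---|---|
| Section 4, Section 8, title of 9.2.1.3 | all bDMARDs and all tsDMARDs |
| Censoring bullet in 9.2.1.3 | tofacitinib and bDMARDs only |
| Section 9.4.3; Appendix 2 Tables I and II | biologics only |

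The set left between the first two rows is every tsDMARD other than tofacitinib.

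**Step 2. Does another rule close the gap?**

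- Section 9.3.2 follows subjects to the outcome "with death and emigration from Sweden treated as censoring events". No start of therapy is added.
- The once-exposed-always-at-risk analysis in Section 9.3.2 ends follow-up at the event, loss to follow-up, death or end of study. Again there is no therapy start.
- Section 9.2.2 says only "Patients not meeting the inclusion criteria for the respective cohorts will be excluded". The bullets of 9.2.1.3 do not restate naivety as an entry criterion, so this adds nothing beyond the title.

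No other rule closes it.

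**Step 3. Are such drugs foreseen?** Yes. The secondary analysis censors the bDMARD cohort at them, and a sensitivity analysis in Section 9.3.2 restricts that cohort to patients never exposed to them. Ending tofacitinib follow-up only at a switch outside the JAK class recognises other JAK inhibitors.

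**Step 4. Illustration of size.** The protocol has no figure to reproduce: it gives no uptake of other tsDMARDs, and Tables 2 and 3 concern tofacitinib versus bDMARD only. The inputs below are therefore assumptions.

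- f: share of naive person-time that follows the start of another tsDMARD (assumed 1% to 20%).
- HR: true ratio of tofacitinib to a truly naive cohort. The other tsDMARD is assumed to have the same ratio, at once. The value 2 is borrowed from Section 9.5, where it is the planning effect for tofacitinib versus bDMARD, not versus this cohort.

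With a truly naive rate r, the mixed comparator rate is r(1 − f) + r·HR·f = r[1 + f(HR − 1)]. Hence

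observed HR = HR / [1 + f(HR − 1)].

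For HR = 2: 2/1.01 = 1.98, 2/1.05 = 1.90, 2/1.10 = 1.82 and 2/1.20 = 1.67.

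| True HR | f = 1% | f = 5% | f = 10% | f = 20% |
|---|---|---|---|---|
| 1.5 | 1.49 | 1.46 | 1.43 | 1.36 |
| 2.0 | 1.98 | 1.90 | 1.82 | 1.67 |
| 3.0 | 2.94 | 2.73 | 2.50 | 2.14 |

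**The case against.** The strongest reply is that the definition already carries the condition. Someone who starts another tsDMARD is no longer naive under the title, abstract and objectives. The bullet can be read as a rule for moving between study cohorts, since it goes on to mention entry into the drug-based cohorts and only tofacitinib and bDMARDs have one. This stands as evidence of intent: the gap looks like incomplete drafting. It does not cure the gap, because this bullet is the only therapy-based censoring rule the cohort has. The reply also answers most of any complaint about entry, since naivety at index is stated in the title and objectives and is merely absent from the bullets.

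A second reply is that leakage is probably small. Section 9.3.2 expects tofacitinib to be used as later-line treatment. If other tsDMARDs are used in the same way (an assumption), most of their users will already have left the naive cohort at a bDMARD start. What remains is patients whose first advanced drug is another tsDMARD, until they start tofacitinib or a bDMARD. This is plausible and stands.

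A third reply is that the formula is generous. It gives the other drug tofacitinib's full effect immediately, while Section 9.3.2 expects malignancy to appear with a delay. This also stands, so the table is an illustration and not an estimate.

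Finally, the cohort is mainly contextual, and Section 9.7.2 ties the decision on formal comparison to tofacitinib versus bDMARDs. That limits the consequence.

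**Conclusion.** The point holds as a contradiction between a clear definition and an incomplete censoring rule, which should be corrected. The direction toward no difference rests on other tsDMARDs sharing tofacitinib's effects. The size rests on an uptake that the protocol does not give, and may be small: 1.98 or 1.90 in place of 2 at an assumed 1% or 5%.

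A reader might infer more, but the protocol does not support it:

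- *That keeping these patients was a deliberate choice.* The title, abstract and objectives point the other way.
- *That the bias is material or grows over calendar time.* No uptake or trend in other tsDMARDs is given.
- *That the bDMARD cohort is always censored at these drugs.* That holds only in the secondary analysis. In the primary analysis of malignancy and mortality, follow-up continues after a switch.
- *That every outcome affected belongs to the June 2021 signal procedure.* Section 7 gives that procedure as MACE and malignancies excluding NMSC. VTE was dealt with separately in 2019 (Section 7.3).
- *That the main drug comparison is compromised.* The tofacitinib-versus-bDMARD contrast does not use this cohort.

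**What to change.** 1. Reword the bullet in Section 9.2.1.3 so that patients are censored at the first start of any bDMARD or any tsDMARD, and may enter a drug-based cohort only where its own criteria are met. A patient who starts a tsDMARD other than tofacitinib then leaves the naive cohort without entering a drug cohort at that point.
2. Add a bullet requiring no bDMARD or tsDMARD before index, checked in SRQ and the Prescribed Drug Register. Section 9.4.3 already allows the latter to be used for classifying patients by DMARD history.
3. Align the wording that speaks of biologics only: the description of the diagnosis-defined comparators in Section 9.4.3 and the row and column labels in Appendix 2 Tables I and II.

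The cost is a sentence or two, a small change to the cohort code and some relabelling. The person-time lost is exactly the share f, none of which belongs in the cohort. Reporting how much time the new rule removes would also show how large the problem would have been.
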